Each CHW will collaborate with church leaders (see study sites and letters of support) to organize depression screening events at church health-focused programs. Two CHWs and at least one Project Coordinator (PC) will be present at the church for each screening event to assist with scoring the Patient Health Questionnaire-9 (PHQ-9), interpreting the results, and study enrollment. Eligibility for depression screening include: 1) Adults 18 years and older; and 2) English-speaking. There are no exclusion criteria for general depression screening. The screening will occur in a private space in the church to protect participant confidentiality. The screening survey will include the PHQ-9 and demographic information. Participants will submit their completed survey to the CHW in a private church space, who will quickly assess for suicidality by examining responses to Question #9 of the PHQ-9. Eligibility for the Randomized Controlled Trial (RCT) depends on the participants' total PHQ-9 score:

- Participants whose PHQ-9 9 (negative depression screen), are ineligible for the RCT and will receive a copy of Mental Health Resources.

- Participants whose PHQ-9 10 (positive depression screen), will be eligible for the RCT and invited to sign informed consent to participate in the study.

Page 12 of 25

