Intervention arm: [(Screening + Brief Intervention + Referral to Treatment), n=15 churches]. CHWs will provide two Motivational Interviewing (MI) sessions in each of the first three months, for a maximum of 6-MI sessions over 3 months (Table 1). The initial two sessions will be conducted in person at the church and follow-up sessions will occur either in-church or over the phone. Data will be collected on method of delivery. MI sessions will create a nonjudgmental and supportive environment for eligible participants to move through the various stages of change associated with depression help-seeking. In the initial session, CHWs will focus on establishing rapport using openended guestions, affirmations, reflections, and summary statements (OARS). They will then review depression symptoms based on the participants PHQ-9 score. The second session will focus on assessing motivation and confidence in seeking treatment and elicit barriers and facilitators for depression treatment. Follow-up sessions will involve summarizing the 'pros' and 'cons' of depression treatment; providing options for the participant based on the nature of barriers elicited from them; assessing participant's values and goals, to help them link their current mental health pattern to their goals; and summarizing what was discussed to clarify an action plan. The final component of SBIRT involves actual referrals to treatment. This begins with determination of the individual's health insurance status. Persons without insurance will be enrolled with the assistance of CHWs (who are certified New York State Insurance Navigators) into New York State health plans (insurance exchange or Medicaid). Based on our preliminary studies, we expect 12 to 15% of subjects to be uninsured. Individuals ineligible for health insurance will be referred to our network of free clinics providing mental health services. Uninsured individuals will also be referred to the NYC Dept. of Health Action Centers, to insurance information, and other social services (see Letters of Support). Referral involves the CHW calling (using study-issued prepaid calling cards) or offering to call the provider's office on behalf of the subject to make an appointment, plus a follow up appointment call reminder the day before the appointment.

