Usual Care arm: [Referral as Usual (RAU), n=15 churches]. Distributing depression educational materials and contact information for treatment providers is the most common form of referral. This practice will represent "usual care" for our study. We will utilize depression educational brochures describing the nine hallmark symptoms of depression symptoms and the importance of seeking treatment: one from the National Institute of Mental Health (NIMH), one from the American Psychiatric Association (APA), and one from National Alliance of Mental Illness (NAMI). CHWs assigned to usual care churches will distribute the list of referral sites and pamphlets to study participants at designated

screening events. No specific referrals will be made in this arm.

Page 13 of 25

Assessments. Within two weeks of completing the PHQ-9 and study enrollment, Project Coordinators will conduct telephone baseline assessments with participants who signed informed consent. Table 3 shows the name and construct for each clinical measure collected at baseline, 3-months, and 6-months post screening.

VIRTUAL STUDY PROCEDURES

Considering COVID-19 and the New York State on Pause law, we will also conduct study procedures virtually. Study Project Coordinators will facilitate Columbia-HIPPA compliant Zoom screening events with church members from approved church study sites. The same study procedures outlined above will be followed, however, the interaction will be conducted via Zoom.

Recruitment And Consent

Recruitment:

Will you obtain information or biospecimens for purposes of screening or determining eligibility? No

Describe how participants will be recruited:

This study involves three distinct study populations.

(1) Clergy (n=30): The lead pastor of each church study site will be recruited for participation in a semi-structured interview. The purpose of the interview is to explore clergy's perspectives of church-based depression screening and awareness of CHW activities in their church. Clergy will received a \$100 gift card as compensation in the interview.

(2) Community Health Workers (n=60): CHWs form Columbia's Training Program will be eligible for participation in focus groups. The purpose of the focus groups is to identify barriers and facilitators of SBIRT (intervention) implementation and factors that would contribute to long-term sustainability of the intervention in churches. CHWs will receive \$25 for participation in focus groups

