Data Safety Monitoring Plan. In compliance with NIH requirements, we will establish a data and safety monitoring plan (DSMP). The purpose of these plans is to ensure the safety of participants and the validity and integrity of the data. Considering the study rationale, population, procedures, and the risk: benefit profile as outlined; the overall risk level for participation in this screening intervention is classified as minimal. Due to the classification of this study as minimal risk, the following members of the investigative team will serve as the Data Safety Monitoring Committee and will perform the monitoring: [name], Contact-Principal Investigator (Columbia University, Dept. of Psychiatry). [name] will be responsible for corresponding with NIMH. In addition to providing timely reports to NIMH, regarding (i) Unanticipated problems or unexpected serious adverse events that may be related to the study protocol, (ii) IRB-approved revisions to the study protocol that indicate a change in risk for participants, and (iii) Notice of any actions taken by the IRB or regulatory bodies regarding the research and any responses to those actions, [name] will be responsible for: Reviewing all PHQ-9 questionnaires and assessments by participants students at baseline, 3-, and 6months; Reviewing safety plans documented by CHWs; and Reviewing rates of participant referral to treatment.[name], Multiple-Principal Investigator (Columbia University, Dept. of Neurology). [name] will provide site oversight by auditing CHW protocols and church sites where the intervention and control programs will take place. In addition to intervention fidelity monitoring, [name] will perform random interviews with CHWs (at least once at each church site) to evaluate the presence of any adverse reactions to the curriculum that may not be captured by questionnaire data. [name], Co-Investigator (Hebrew Home at Riverdale). [name] is the head project statistician at the Research Division of the Hebrew Home at Riverdale. She and her team will act as the Data Coordinating Center (DCC) and regularly review program data, which will be discussed with the MPIs monthly. These data will include guestionnaire items designed to capture adverse student emotional responses to the intervention. [name] has directed over 100 DCCs for single and multi-site projects, and has served on many DSMBs.Project Director – TBN. The Project Director will be present on site at every intervention and control program. In addition to project management activities such as recruitment, consenting, training, and data collection, the PD will be responsible for identifying and reporting any adverse encounters - related or unrelated to the intervention - to the Multi-PIs. These include adverse emotional responses, interpersonal conflicts, physical accidents or any other participant safety concerns that may occur during the intervention. Monitoring Study Safety: The data and safety monitoring plan will consist of reporting of adverse events to the IRB and to NIH trials. Adverse events will be reported to the Columbia IRB, which has the authority to halt the trial if it perceives that harm is occurring due to the intervention. Summaries of adverse events reports will be made to NIH in the yearly progress report and at the end of year 5, in the final report, unless the nature of a particular event is such that it bears reporting to NIH immediately. The progress of the trial will also be evaluated from the initial screening of participants by inclusion and exclusion criteria to the informed consent process to the provision of participant study instruction to staff training in Good Clinical Practices (GCP) and regulations pertaining to the Conduct of Human Participant Research. This will also include internal monthly quality control audits, periodic assessments of data quality and timeliness,

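### Adverse events are to be found by an on-site Project Director and by items written for students, which does not suit a trial with phone and Zoom contacts and unequal contact between arms

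*Protocol*

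**What the plan says.** Data and Safety Monitoring names several routes by which harm could come to light.

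- **Project Director.** "The Project Director will be present on site at every intervention and control program". This role is to identify and report adverse encounters, whether or not related to the intervention. The examples given end with "physical accidents or any other participant safety concerns that may occur during the intervention".
- **Questionnaire.** The data coordinating centre reviews data that include "items designed to capture adverse student emotional responses to the intervention". The instrument holding these items is not named.
- **Contact PI.** Reviews all PHQ-9s and assessments at baseline, 3 and 6 months, the safety plans that CHWs document, and rates of referral.
- **Second PI.** Interviews CHWs, at least once per church, about adverse reactions to the curriculum that questionnaires may miss.

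A suicidality plan (Safety Assessment, under Procedures and under Potential Risks) is triggered by what a participant says or by the PHQ-9. Adverse events go to the IRB, "which has the authority to halt the trial if it perceives that harm is occurring due to the intervention".

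On how contacts take place, the Intervention arm text puts the first two MI sessions in church, while "follow-up sessions will occur either in-church or over the phone". The Assessments text makes the baseline assessment a telephone call by Project Coordinators. Virtual Study Procedures adds: "Considering COVID-19 and the New York State on Pause law, we will also conduct study procedures virtually". Usual-care participants receive pamphlets and a list of referral sites at the screening event and have no MI sessions.

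**The concern.** An observer on site cannot see a phone call or a Zoom session, and the section does not make the staff who conduct those contacts responsible for reporting events. The student wording does not describe this population, so it is unclear what the questionnaire route will ask, or of whom.

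The arms also differ by design in how often anyone meets a participant. If events are found by watching and by unprompted report, the arm with more contact has more chances to have an event recorded, even when the true rates are equal. The IRB is asked to perceive harm due to the intervention, and that judgement is weaker when the extra events in one arm may reflect extra contact. Events away from any program, such as an emergency visit between sessions, depend on whether some form happens to ask about them.

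**Working it through.** The protocol gives no figure on this point, so there is nothing to reproduce. The check sets routes against contacts and then counts contacts.

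**1. Routes against contacts**

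| Route | Reaches phone or Zoom contacts? | Same in both arms? |
|---|---|---|
| Project Director on site | No | Not if MI sessions count as programs |
| Emotional-response items | Cannot be told; instrument not named | Cannot be told |
| Review of PHQ-9s and assessments | Yes | Yes |
| Suicidality plan and safety plans | Yes, suicidality only | Same trigger, but more CHW contacts under SBIRT |
| Interviews with CHWs | Indirectly, perhaps once per church | Usual-care CHWs have no scheduled participant contact after screening |

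**2. Instruments.** The Documents list includes the PHQ-9, QIDS, PROMIS Depression, SF-12, C-SSRS, a health-services form and others. No title is identifiable as an adverse-event or reaction form. The instruments and Table 3 are not shown, so this is a statement about titles only.

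**3. Contacts per participant** (church screening, all six MI sessions attended)

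Inputs: 1 screening event; 3 assessments in both arms; up to 6 MI sessions under SBIRT, 2 in church and 4 in church or by phone. Appointment-reminder calls are left out; they would add to the SBIRT count. The baseline assessment is by telephone and the mode of the later two is not stated, so assessments are not counted as on site.

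- On site, SBIRT: 1 + 2 = 3 if four sessions are by phone; 1 + 6 = 7 if none are.
- On site, usual care: 1. Ratio 3 to 7.
- All scheduled contacts: SBIRT 1 + 6 + 3 = 10; usual care 1 + 3 = 4. Ratio 10/4 = 2.5.

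With 600 participants split evenly (an assumption), 300 are in SBIRT. Up to 300 × 4 = 1,200 MI sessions could then be out of an on-site observer's view. In-church MI sessions number from 300 × 2 = 600 to 300 × 6 = 1,800. With 300/15 = 20 participants per church, that is 40 to 120 per church.

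**4. What the imbalance could do (illustration only).** Let q be the chance that one contact produces a record, equal in both arms, and k the number of contacts. The chance of at least one record is 1 − (1 − q)^k. The protocol gives no q, so the values are assumed.

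| q | SBIRT, k = 10 | Usual care, k = 4 | Ratio | On-site only, 3 v 1 | On-site only, 7 v 1 |
|---|---|---|---|---|---|
| 0.02 | 18.3% | 7.8% | 2.36 | 2.94 | 6.59 |
| 0.05 | 40.1% | 18.5% | 2.16 | 2.85 | 6.03 |
| 0.10 | 65.1% | 34.4% | 1.89 | 2.71 | 5.22 |
| 0.20 | 89.3% | 59.0% | 1.51 | 2.44 | 3.95 |

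The direction is the same throughout, but the size depends wholly on q and on which contacts count.

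**The case against.** Several stronger readings are tempting, and the protocol does not support them.

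- **Remote contacts are not covered at all.** Too broad. The suicidality plan is not tied to being on site, the Zoom text says the same procedures apply, the contact PI reviews every assessment, and CHW interviews reach the people who deliver phone sessions. Only the Project Director route depends on place.
- **Nothing is asked equally in both arms.** Not so. PHQ-9 and assessment review at baseline, 3 and 6 months is not limited to one arm, and the PHQ-9 includes a suicidality item. What is not identified is an equal question about other harms.
- **The Project Director looks only for events during the intervention.** The duty covers related and unrelated events, in control programs too; the narrower words come in a list of examples.
- **The Project Director is absent from screening.** The staffing rule, "Two CHWs and at least one Project Coordinator (PC) will be present at the church for each screening event", does not exclude that role.
- **A definite excess, such as 3.5-fold.** Detection of 70% against 20% gives 0.70/0.20 = 3.5, but that only restates two assumed rates.
- **The safety comparison is invalid.** The protocol states no between-arm event comparison. It classes the trial as minimal risk and plans monthly data discussion and early safety reviews.

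Also, program is not defined. If it means screening events only, the Project Director sees 1 contact in each arm and that part of the imbalance disappears, but then no MI session is observed. The health-services form may record emergency visits; its content is not shown and the monitoring text does not name it as a source of adverse events.

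These points narrow the concern. They do not fit the on-site rule to phone and Zoom contacts, explain the student items, or equalise unprompted reporting.

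**Conclusion.** The concern holds in a limited form. Two of the stated means of finding adverse events do not suit this trial: the Project Director route depends on presence that phone and Zoom contacts do not allow, and the questionnaire route is described for a population that is not enrolled. Suicidality is better covered than other harms.

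For those other events, recording is likely to be more frequent under SBIRT because of contact alone, which weakens the IRB's basis for attributing harm to the intervention without removing it. The contact imbalance can be counted: 3 to 7 against 1 on site, up to 10 against 4 overall. This assumes church screening and full MI attendance; the on-site count also assumes that MI sessions are programs. The resulting imbalance in recorded events cannot be derived. This is a worthwhile, inexpensive improvement and does not show that the trial's safety oversight fails.

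**What to change.** In Data and Safety Monitoring:

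1. Replace the student wording with wording for adult participants, and name the instrument that holds the items.
2. Rewrite the on-site rule so that whoever conducts an in-church, phone or Zoom contact is responsible for reporting events to the Multi-PIs.
3. Add one short structured adverse-event question set, for example emergency visit, hospital admission, self-harm, distress from study contact and breach of privacy. Ask it identically in both arms at the existing 3- and 6-month assessments, covering the whole interval since the last assessment.
4. Report the answers by arm to the IRB and NIH, and list spontaneous reports separately so that differences in contact are not mixed into the comparison.

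The existing suicidality procedures are untouched. The cost is an edit to the monitoring text and a few questions at two assessments already planned; the downside is a slightly longer interview.
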